1.2.11 EP0057 (CRLX101) Clinical Development Overview

As of 12 March 2016, there have been 5 clinical trials sponsored by Cerulean: CRLX-001, CRLX-002, CRLX101-208, CRLX101-209, and CRLX101-102.

- Studies CRLX-001 and CRLX-002 have been completed; studies CRLX101-208, CRLX101-209, and CRLX101-102 are ongoing.
- 246 subjects received CRLX101/EP0057 at doses ranging from 6 to 18 mg/m² in the 5 cerulean-sponsored trials.

There have been 7 Investigator-sponsored trials (ISTS) with EP0057 (named CRLX101 at the time), (see **Table 4** for details); as of 12 March 2016, 138 subjects received at least 1 dose of EP0057 in the ISTs at doses ranging from 12 to 15 mg/m².

- A total of 384 subjects across all studies have received at least 1 dose of CRLX101. When tested in the QOW schedule, the MTD/RP2D of EP0057 monotherapy was determined to be 15 mg/m².
- EP0057 has been generally well-tolerated, and has shown preliminary antitumor activity in subjects with solid tumors such as with gastroesophageal, lung, and ovarian cancers.

As of 12 March 2020, there have been 6 clinical trials sponsored by Cerulean Pharma (prior to 17 April 2017) and BlueLink Genetics (as of 17 April 2017). Overall, 286 subjects received at least 1 dose of EP0057 at doses ranging from 6 to 18 mg/m² in these 6 BlueLink Genetics-sponsored studies. There have been 8 Investigator-sponsored trials with EP0057 in which 193 subjects received at least 1 dose of EP0057 at starting doses ranging from 12 to 15 mg/m². When tested in the every-other-week schedule, the MTD/recommended phase 2 dose (RP2D) of EP0057 monotherapy was determined to be 15 mg/m². EP0057 has been generally well-tolerated, and has shown preliminary antitumor activity in subjects with solid tumors.

Overall Safety Assessment from these trials indicated:

- Infusion-related reactions, cystitis, hematologic toxicity, and gastrointestinal disorders have been recognized as the risks associated with EP0057.
- Infusion-related hypersensitivity reactions have been well managed with the mandatory premedication and slower rate of infusion.
- Cystitis symptoms have been well managed with IV hydration before and after the EP0057 infusion. In addition, the impact of urine alkalization (oral and/or IV) on the incidence and severity of cystitis in subjects treated with EP0057 continue to be evaluated.

EP0057 is contraindicated for subjects who have a history of infusion-related hypersensitivity reactions to a topo-1 inhibitor or any EP0057 excipients. The effects of EP0057 on the developing human fetus or concentration in breast milk with respect to nursing mothers are unknown. Olaparib

Olaparib is a PARP inhibitor indicated as monotherapy in patients with deleterious or suspected deleterious germline BRCA mutated (as detected by an FDA-approved test) advanced ovarian

cancer who have been treated with three or more prior lines of chemotherapy. Olaparib has an established safety profile and it is under investigation in a number of different cancers.

Olaparib (AZD2281, KU-0059436) is a potent Polyadenosine 5'diphosphoribose [poly (ADP ribose) polymerisation (PARP) inhibitor (PARP-1, -2 and -3) that is being developed as an oral therapy, both as a monotherapy (including maintenance) and for combination with chemotherapy and other anti-cancer agents.

PARP inhibition is a novel approach to targeting tumors with deficiencies in DNA repair mechanisms. PARP enzymes are essential for repairing DNA single strand breaks (SSBs). Inhibiting PARPs leads to the persistence of SSBs, which are then converted to the more serious DNA double strand breaks (DSBs) during the process of DNA replication. During the process of cell division, DSBs can be efficiently repaired in normal cells by homologous recombination repair (HR). Tumors with HR deficiencies (HRD), such as serous ovarian cancers and SCLC cannot accurately repair the DNA damage, which may become lethal to cells as it accumulates. In such tumor types, olaparib may offer a potentially efficacious and less toxic cancer treatment compared with currently available chemotherapy regimens.

[figure not shown]
[figure not shown]
Olaparib has been shown to inhibit selected tumor cell lines in vitro and in xenograft and primary explant models as well as in genetic BRCA knock-out models, either as a stand-alone treatment or in combination with established chemotherapies. Cells deficient in homologous recombination DNA repair factors, notably BRCA1/2, are particularly sensitive to olaparib treatment.

PARP inhibitors such as olaparib may also enhance the DNA damaging effects of chemotherapy ([50-52](#)). For further information, please refer to the current version of the olaparib Investigator Brochure.

1.2.12 Preclinical Data of EP0057 (CRLX101) plus Olaparib

In vivo studies (conducted by Astra Zeneca) show that concurrent combination of EP0057 and olaparib resulted in a dose-dependent decrease in hematological parameters in preclinical rat bone marrow model ([53](#)). However, combination with delay (24h+) between EP0057 and olaparib provided sparing effect on peripheral blood cells (nadir and recovery) ([Figure 3](#)).

The combination of EP0057 with olaparib (starting 24 hours after EP0057) administered for 14 days had significantly more anti-tumor activity than olaparib administered for 2 days and provided greater efficacy than EP0057 alone ([Figure 4](#)). The combination was also significantly more efficacious than topotecan (standard-of-care for SCLC).

1.2.13 Hypothesis

Despite their highly synergistic activity in preclinical models, human studies combining PARP inhibitors and camptothecins have not translated into clinical benefit due to enhanced toxicity with the combination. EP0057 (and free camptothecin) is cleared out more slowly from tumor cells compared to plasma/bone marrow and induces sustained activation of DNA damage response in tumor. Of note, in preclinical models, most EP0057 is cleared from the bone marrow by 24 hours; in contrast, durable topoisomerase 1 inhibition in the tumor is apparent. This effect combined with low systemic exposure lends EP0057 to combinations with PARP inhibitors where both drugs can potentially be used at effective doses. Based on preclinical studies, PARP inhibitors used 48 hours after EP0057 administration will provide synergy while minimizing risk of myelosuppression.

1.2.14 Rationale

PARP inhibitors are highly synergistic in combination with camptothecins in preclinical models. However, this has not translated to clinical effectiveness, primarily due to enhanced toxicity which precludes administration of effective doses of either the PARP inhibitor or chemotherapy. Major dose limiting toxicity of this combination is myelosuppression. EP0057 is a nanoparticle drug conjugate with a camptothecin payload that provides durable inhibition of topoisomerase I (Top1) specifically in the tumor. EP0057 is cleared from the bone marrow relatively quickly. These properties allow combination of EP0057 with PARP inhibitors where both drugs can potentially be used at doses close to the MTD of each. Based on preclinical studies, PARP inhibitors used 48 hours after EP0057 and continued for 11 days will provide maximum synergy while minimizing risk of myelosuppression.

Since the safety of this combination is not established, we propose a phase I trial where escalating doses of olaparib will be combined with EP0057 administered at 80% of its MTD (12 mg/kg IV q2 weeks). The starting dose of olaparib is 100 mg bid which is a third of its single-agent maximum tolerated dose (MTD; 300 mg tablet BID).

1.2.16 Rationale for Amendment E

Summary of Dose Escalation and Determination of MTD/Recommended Phase II Dose

Twenty-four patients were enrolled between May 2016 and December 2017. All patients had received one or more lines of prior systemic therapy and had evidence of disease progression at enrollment.

Patients across different dose levels received the same dose of EP0057 (EP0057 12mg/m² Q2W) and increasing doses of olaparib. There were no DLTs at DL1 (n=3; olaparib 100 mg BID), DL2 (n=5, 2 patients were not evaluable for DLT; olaparib 150 mg BID), or DL3 (n=3; olaparib 200 mg BID). One patient at DL4 (olaparib 300 mg BID) experienced a DLT- grade 4 neutropenia not recovering within 7 days. This cohort was expanded with 5 additional patients. One additional patient had a DLT at this dose level- inability to begin subsequent treatment course within 28 days of the scheduled date, due to neutropenia. Therefore, DL4 was considered too toxic and 3 patients were enrolled at DL4R with lower dose of olaparib 250 mg BID. One of the 3 patients enrolled at DL4R with lower dose of olaparib had a DLT- grade 4 neutropenia that did not resolve within 7 days. This cohort was expanded with 3 additional patients. No DLTs were observed in the additional patients, which established DL4R (EP0057 12 mg/m² and olaparib 250 mg) as the MTD/RP2D.

1.2.17 Rationale for mCRPC cohort accrual closure (amendment version date: 07/27/2021)

Accrual to the mCRPC cohort is to cease with amendment version date 7/27/2021. Accrual to this cohort has been slow given the recent FDA approval of olaparib for prostate cancer. Additionally, underlying conditions such as history of pelvic irradiation or surgery predispose the prostate cancer cohort to cystitis and hematuria.

1.2.18 Rationale for urothelial carcinoma cohort accrual closure (amendment version date: 08/17/22)

Accrual to this cohort has been slow due to currently active protocols competing for the same patient population. There are also protocols in development which the team believes are better suited for these patients. The decision was made to close cohort accrual on this trial to prioritize current and upcoming studies.

2 ELIGIBILITY ASSESSMENT AND ENROLLMENT

2.1 ELIGIBILITY CRITERIA

2.1.1 Inclusion Criteria - Phase I

- 2.1.1.1 Patients must have histologically or cytologically confirmed advanced solid tumor that is resistant or refractory to standard therapy.
- 2.1.1.2 A minimum of 2 weeks will be required from any prior therapy, including chemotherapy, immunotherapy and/or radiation. In addition, recovery to Grade ≤ 1 from all reversible toxicities related to prior therapy is required at study entry.
- 2.1.1.3 Patients do not need to have measurable disease to enroll on phase I.
- 2.1.1.4 Age ≥ 18 years.
- 2.1.1.5 ECOG performance status ≤ 2 ([Appendix A](#), Section 16.1).
- 2.1.1.6 Patients with treated brain metastases (surgery, whole or stereotactic brain radiation) are allowed provided the lesions have been stable for at least 2 weeks and the patient is off steroids or is on a stable dose of steroids. Patients with brain metastases should not require use of enzyme-inducing antiepileptic drugs (e.g., carbamazepine, phenytoin, or phenobarbital) within 14 days before first dose and during study. Use of newer

antiepileptics that do not produce enzyme induction drug-drug interactions (DDIs) is allowed.

2.1.1.7 Patients must have normal organ and marrow function as defined below:

– leukocytes	$\geq 3,000/\text{mcL}$
– absolute neutrophil count	$\geq 1,500/\text{mcL}$ without growth factor support
– platelets	$\geq 100,000/\text{mcL}$ without growth factor support
– hemoglobin	$\geq 9 \text{ g/dL}$, and no blood transfusion within 4 weeks.
	OR
– hemoglobin	$>10 \text{ g/dL}$, and no blood transfusion within 2 weeks.
– total bilirubin	$\leq 1.5 \times \text{ULN}$ (unless Gilbert's Disease)
– AST(SGOT)/ALT(SGPT)	$\leq 2.5 \times$ institutional upper limit of normal ($\leq 5 \times \text{ULN}$ if liver mets)
– creatinine	$\leq \text{ULN}$
	OR
– creatinine clearance	$\geq 51 \text{ mL/min}$ (calculated using the Cockcroft-Gault formula) for patients with creatinine levels above institutional normal.

2.1.1.8 Individuals who can father children and their partners must agree to use highly effective contraception (refer to section 4.2 for details) prior to study entry, for the duration of study participation and for 3 months following last dose of study drugs. Individuals who are of childbearing potential and sexually active must agree to the use of 1 highly effective form of contraception, and their partners, if they can father children, must use a condom, or they must totally/truly abstain from any form of sexual intercourse, throughout their participation in the study and for at least 6 months after last dose of study drugs. Individuals should not donate sperm throughout the period of taking olaparib and for 3 months following the last dose of olaparib. Individuals of childbearing potential (IOCBP) are defined as being physically capable of becoming pregnant unless unable to have children because of surgery or other medical reasons (effective tubal ligation, ovaries or the uterus removed, or are post-menopausal). Post-menopausal is defined as:

- Amenorrheic for 1 year (12 months in a row) or more following cessation of exogenous hormonal treatments,
- LH and FSH levels in the post-menopausal range for individuals under 50,
- radiation-induced oophorectomy with last menses >1 year ago,
- chemotherapy-induced menopause with >1 year interval since last menses,
- or surgical sterilization of participant (bilateral oophorectomy or hysterectomy) and/or partner.

2.1.1.9 Negative urine pregnancy test ≤ 3 days prior to C1D1 (IOCBP)

2.1.1.10 Patient is willing and able to comply with the protocol for the duration of the study including undergoing treatment and scheduled visits and examinations including follow up.

2.1.2 Inclusion Criteria - Phase II SCLC

2.1.2.1 Age ≥ 18 years.

2.1.2.2 Patients must have histologically or cytologically confirmed diagnosis of SCLC from a CLIA-certified laboratory.

2.1.2.3 Have received and progressed during or after a platinum-based standard chemotherapy regimen and/or an immune-checkpoint inhibitor

2.1.2.4 Patients could have received any number of therapies for relapsed or progressive disease, including re-treatment with original frontline regimen. A minimum of 2 weeks will be required from any prior therapy, including chemotherapy, immunotherapy and/or radiation. In addition, recovery to Grade ≤ 1 from all reversible toxicities related to prior therapy is required at study entry. No previous irradiation to the site of measurable or evaluable disease, unless that site had subsequent evidence of progression.

2.1.2.5 Patients must have measurable disease as per Response Evaluation Criteria in Solid Tumors, version (RECIST 1.1). See Section 6.3 for the evaluation of measurable disease.

2.1.2.6 Radiographic evidence of disease progression after initial therapy should have been documented.

2.1.2.7 ECOG performance status ≤ 2 (see [Appendix A](#), Section 16.1).

2.1.2.8 Patients with treated brain metastases (surgery, whole or stereotactic brain radiation) are allowed provided the lesions have been stable for at least 2 weeks and the patient is off steroids or is on a stable dose of steroids. Patients with brain metastases should not require use of enzyme-inducing antiepileptic drugs (e.g., carbamazepine, phenytoin, or phenobarbital) within 14 days before first dose and during study. Use of newer antiepileptics that do not produce enzyme induction drug-drug interactions (DDIs) is allowed.

2.1.2.9 Patients must have normal organ and marrow function as defined below:

- leukocytes	$\geq 3,000/\text{mcL}$
- absolute neutrophil count	$\geq 1,500/\text{mcL}$ without growth factor support
- platelets	$\geq 100,000/\text{mcL}$ without growth factor support
- hemoglobin	$\geq 9 \text{ g/dL}$, and no blood transfusion within 4 weeks.

OR

- hemoglobin	$>10 \text{ g/dL}$, and no blood transfusion within 2 weeks.
--------------	---

- total bilirubin	$\leq 1.5 \times$ ULN (unless Gilbert's Disease)
- AST(SGOT)/ALT(SGPT)	$\leq 2.5 \times$ institutional upper limit of normal ($\leq 5 \times$ ULN if liver mets)
- creatinine	\leq ULN
OR	
- creatinine clearance	≥ 51 mL/min (calculated using the Cockcroft-Gault formula) for patients with creatinine levels above institutional normal.

2.1.2.10 Individuals who can father children and their partners must agree to use highly effective contraception (refer to section 4.2 for details) prior to study entry, for the duration of study participation and for 3 months following last dose of study drugs. Individuals who are of childbearing potential and sexually active must agree to the use of 1 highly effective form of contraception, and their partners, if they can father children, must use a condom, or they must totally/truly abstain from any form of sexual intercourse, throughout their participation in the study and for at least 6 months after last dose of study drugs. Individuals should not donate sperm throughout the period of taking olaparib and for 3 months following the last dose of olaparib. Individuals of childbearing potential (IOCBP) are defined as being physically capable of becoming pregnant unless unable to have children because of surgery or other medical reasons (effective tubal ligation, ovaries or the uterus removed, or are post-menopausal). Post-menopausal is defined as:

- Amenorrheic for 1 year (12 months in a row) or more following cessation of exogenous hormonal treatments,
- LH and FSH levels in the post-menopausal range for individuals under 50,
- radiation-induced oophorectomy with last menses >1 year ago,
- chemotherapy-induced menopause with >1 year interval since last menses,
- or surgical sterilization of participant (bilateral oophorectomy or hysterectomy) and/or partner.

2.1.3 Inclusion Criteria for Urothelial Carcinoma Expansion Cohort (accrual to the cohort ended with amendment version 08/17/2022)

2.1.3.1 Patients must have a histologically confirmed diagnosis of urothelial carcinoma of the bladder, urethra, ureter, or renal pelvis from a CLIA-certified laboratory, with measurable disease by RECIST (version 1.1) including lymphadenopathy and visceral metastatic disease

2.1.3.2 Adult patients ≥ 18 years of age.

2.1.3.3 Patient must have received at least one platinum based regimen of chemotherapy and/or an immune-checkpoint inhibitor if appropriate with progressive disease.

2.1.3.4 Prior antiangiogenic and radiation therapy are permitted (2-week washout from therapy is required).

2.1.3.5 Bisphosphonates and denosumab are permitted if on a stable dose for ≥ 4 weeks.

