⁷ Includes Alkaline Phosphatase, ALT/GPT, AST/GOT, Total Bilirubin, Direct Bilirubin

⁸ Only for IOCBP; may be obtained up to 3 days prior to Day 1 of each cycle.

⁹ Blood, plasma, hair and saliva samples will be collected at multiple time points during cycles 1,2 and each cycle thereafter for hair collection (for specific timepoints on correlative samples collection please refer to section 5.1.1 for Phase I and Phase II cohorts, section 5.1.2 for UC expansion cohort and section 5.1.3 for mCRPC expansion cohort). C1D15 timepoint for correlative studies will only be done for Phase II SCLC cohort. Only whole blood will be drawn for that cohort at that timepoint.

¹⁰ Optional biopsies will be obtained at baseline, during the first treatment cycle (approximately 24 hours after the first dose of olaparib) and at disease progression. In the mCRPC cohort, biopsy at baseline is mandatory.

¹¹ PO days 3-13 and days 17-26, as indicated in Section 3.2. There should be at least a 48-hour window between EP0057 and olaparib except dose level 5B which allows the interval to be abbreviated to 24 hours. Olaparib can be taken continuously if EP0057 is missed for any reason.

¹² Performed after every 2 cycles

¹³ Approximately 4 weeks after treatment discontinuation

¹⁴ Only done in cycle 1

¹⁵ Only done in phase 2

¹⁶ Phase 1 portion of the study in cycles 1 and 6 only.

¹⁷ Within 3 months of C1D1.

¹⁹ D15 PKs can be obtained +/- 5 days.

²⁰ Weekly during C1, at every visit for subsequent cycles, and whenever clinically indicated

²¹ Within 4 weeks

²² C2 and all subsequent cycles, Day 1

²³ All patients should get tested at screening. Patients taking warfarin will be monitored at least weekly for C1, then monthly if the INR is stable.

²⁴ Includes Albumin, Calcium, Magnesium and Phosphorus

²⁵ PSA is to be analyzed along with measurable lesions evaluated by CT scan of chest/abdomen/pelvis and technetium 99 bone scan every 3 cycles (every 12 weeks).

²⁶ Hair collection will only be done for Phase I cohorts.

²⁷ ECG required within 60 -180 minutes post-infusion for first two cycles of EP0057 for patients with any conduction abnormality on baseline ECG.

²⁸ Day 15 assessments not required for patients on olaparib only.

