4.2 HIGHLY EFFECTIVE METHODS OF BIRTH CONTROL

The study drugs used in the study are regarded as having with medium/high fetal risk.

Individuals of childbearing potential and their partners, who are sexually active, must agree to the use of one highly effective form of contraception and their partner must use a condom [as listed below]. This should be started from the signing of the informed consent and continue throughout the period of taking study treatment and for at least 6 months after last dose of study drug(s), or they must totally/truly abstain from any form of sexual intercourse (see below).

Individuals who can father children must use a condom during treatment and for 3 months after the last dose of olaparib when having sexual intercourse with a pregnant woman or with a woman of childbearing potential. Their partners should also use a highly effective form of contraception if they are of childbearing potential (as listed below). Individuals who can father children should not donate sperm throughout the period of taking olaparib and for 3 months following the last dose of olaparib.

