10.1 PHASE I AND PHASE II

For the phase I portion of the trial, a standard 3+3 design will be used, to determine the RP2D/MTD of EP0057 in combination with olaparib. The theoretical maximum number of subjects required to determine the MTD in the phase I portion of the study is 30 subjects (6 per dose level), although it is expected that as few as 15 subjects in 4 dose levels would be required to reach an MTD.

Sensitivity to first-line chemotherapy has been considered as the main driver of second-line therapy outcome in SCLC. For this reason, relapsed SCLC has been traditionally classified into sensitive and resistant disease according to the type of response to first-line therapy and to treatment-free interval (treatment-free interval longer or shorter than 60–90 days) (68). Although this definition was derived many years ago and based on a small patient series (69), first-line chemotherapy sensitivity has since been confirmed to be a prognostic factor to predict response to second line and further therapy in meta-analyses (3) and randomized studies (70, 71).

Published results suggest that the median PFS for single agent therapy with topotecan (currently the only approved second line therapy) for previously treated patients which included a combination of sensitive and resistant /refractory SCLC patients was approximately 3 months (median 3.0-4.3 months for sensitive and 1.5-2.6 months for refractory; (68, 70-73) (refer to **Table 15**).

A recent randomized study of PARP inhibitor plus chemotherapy in relapsed SCLC patients (both platinum-sensitive and resistant patients were included) found no significant difference in 4-month PFS between temozolomide/veliparib (20 of 55; 36%) and temozolomide /placebo (13 of 49; 27%; $P = .19$) (74). Median PFS was 3.8 months and 2.0 months in the temozolomide /veliparib and temozolomide /placebo arms, respectively (log-rank $P = .39$; hazard ratio, 0.84; 95% CI, 0.56 to 1.25).

Patients with both sensitive and resistant SCLC will be enrolled in the phase II study and analyzed together. The phase II trial will be conducted using an optimal two-stage design in order to rule out an unacceptably low success rate of 25% ($p_0=0.25$) in favor of an improved success rate of 45% ($p_1=0.45$). With alpha=0.10 (probability of accepting a poor treatment=0.10)

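### The last post-menopausal bullet in SCLC criterion 2.1.2.10 ends with the words and/or partner; read literally, it takes a fertile woman with a sterilised partner out of every mandated pregnancy test

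*Combined protocol and SAP*

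**What the plan says.** Criterion 2.1.2.10 starts from whether a person is physically able to conceive and then makes an exception: "unless unable to have children because of surgery or other medical reasons (effective tubal ligation, ovaries or the uterus removed, or are post-menopausal"). Five bullets then say what post-menopausal means. The first four describe the woman's own state: amenorrhoea, hormone levels, or ovarian loss after radiation or chemotherapy. The fifth is "or surgical sterilization of participant (bilateral oophorectomy or hysterectomy) and/or partner". The same bullet stands in 2.1.1.8 (Phase I, completed) and 2.1.3.8 (urothelial cohort, closed to accrual).

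IOCBP status decides who is tested:

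- Sections 2.3.2 and 3.3.6 ask for a urine or serum HCG test in IOCBP.
- Footnote 8 of the study calendar (3.4) says of the pregnancy test: "Only for IOCBP; may be obtained up to 3 days prior to Day 1 of each cycle". After baseline, the test is marked in the column that footnote 22 defines as "C2 and all subsequent cycles, Day 1".
- Phase I has its own criterion, 2.1.1.9, "Negative urine pregnancy test ≤ 3 days prior to C1D1 (IOCBP"), with the same limit. The SCLC criteria have no counterpart.

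Section 4.2.1 deals with a vasectomised partner in another way. It lists him among the accepted non-hormonal methods, combined with a condom and with the participant's assurance that his azoospermia was confirmed.

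**The concern.** A partner's operation does not change a woman's own ability to conceive. Yet the bullet, joined to the list by *or* and containing *and/or*, can be met by the partner's sterilisation alone. A site that follows the words would class a fertile woman as post-menopausal and would owe her no pregnancy test before or during treatment.

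The tests support exclusion 2.1.5.9, which keeps pregnant individuals out because the drugs may be teratogenic or abortifacient. The exclusion itself orders no test. At stake is a fetal exposure that a required test would have caught.

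**Working it through.** No statistical calculation applies. The check sets the provisions side by side.

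**Literal reading.**
1. The partner is surgically sterilised, so the fifth bullet is met.
2. A bullet is met, so the woman is post-menopausal as defined.
3. Post-menopausal is one of the listed exceptions, so she is not an IOCBP.
4. She is not an IOCBP, so no HCG test is required under 2.3.2, 3.3.6 or calendar footnote 8. The contraception duty for women in 2.1.2.10 and 4.2 does not reach her either.

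**Benign readings.** One is that the opening of the definition controls: she is able to conceive, so she stays an IOCBP whatever the bullet says. Another is that *partner* means the female partner of a male participant, who has had her ovaries or uterus removed. Section 4.2 does ask about such partners: "Their partners should also use a highly effective form of contraception if they are of childbearing potential (as listed below"). On either of these, no test is lost.

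**Does anything else restore the test under the literal reading?**

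| Provision | Depends on IOCBP status? | Requires a test? |
|---|---|---|
| 2.1.1.9, Phase I negative test | Yes | Yes, but not for her |
| 2.1.5.9, pregnancy exclusion | No | No |
| 3.3.6, further analyses where clinically indicated | No | No, permits one |
| 3.6.1, removal from therapy on pregnancy | No | No |
| 8.6.1, pregnancy reporting | No | No |
| 12.1, general contraception statement | No | No |
| 14.2.8, advice on fetal risk | No | No |

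Nothing does. Removal and reporting act only once a pregnancy is known.

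**Tests lost per affected woman.**
- Section 3.3.6 limits the test to screening: 1 required if she is an IOCBP, 0 if not, so the loss is 1.
- The calendar has one test before cycle 1 (footnote 2 waives a baseline repeat when screening was in the window) and one at Day 1 of each later cycle. A woman who starts *k* cycles loses 1 + (*k* − 1) = *k* tests.
- Under either benign reading the loss is 0.

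The difference between 3.3.6 and the calendar is a separate inconsistency. It is used here only to give the minimum and what is added to it.

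**Women affected.** The documents give no count. For scale only, each such woman would be 1/27 = 3.7% of the up to 27 evaluable SCLC patients in 10.1. Zero is possible.

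**Does the fix work under every reading?** With *and/or partner* struck, the bullet covers the participant's own surgery only, so the fertile woman stays an IOCBP. A male participant's partner who has no ovaries or uterus is still outside the group, because the general exception quoted from 2.1.2.10 already names removal of either.

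**The case against.** The best answer is that no sensible site would read the bullet this way. Post-menopausal describes a person's own state, the parenthesis names only female procedures, and the definition opens with physical ability to conceive. The vasectomy entry in 4.2.1 would do little for female participants if a sterilised partner had already removed them from the group. The investigator also remains free to test when clinically indicated and must advise on fetal risk.

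Much of this stands, and it makes the literal reading the less likely one. It does not dispose of it. The parenthesis is attached to the participant, not to the partner. Section 4.2.1 also lists tubal occlusion, although the definition takes a woman with an effective tubal ligation out of IOCBP, so being listed as a method does not by itself show that a woman is still an IOCBP. No provision states which reading governs, and the bullet's own words point the wrong way.

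A reader might go further and infer that the protocol leaves such women unprotected, or permits treatment in pregnancy. The documents do not support that: the pregnancy exclusion, removal on pregnancy, reporting and the general contraception statement in 12.1 all apply regardless of IOCBP status. Nor is a clinical check on the vasectomy lost. Section 4.2.1 asks only for the participant's assurance, and only where vasectomy is the chosen method.

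**Conclusion.** The point holds as a wording error in an eligibility definition that controls a safety test. Under the literal reading, an affected woman loses at least the one required screening HCG test, the later per-cycle tests where the calendar is followed, and the contraception rule for women. Under the benign readings she loses nothing.

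This rests on two things the documents do not settle: whether a site would follow the bullet at its word, and whether any fertile woman with a surgically sterilised partner enters the SCLC cohort. Both make the event unlikely, and the number affected may be zero. It would be wrong to infer that the sponsor meant to exempt these women, since the opening clause and 4.2.1 point the other way. It would also be wrong to infer any statistical consequence: the primary endpoint, sample size and error rates do not depend on this definition. Because the possible harm is serious and the correction very small, it should be made in the next amendment.

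**What to change.** Strike *and/or partner* from the last post-menopausal bullet in 2.1.2.10 and, for consistency, in 2.1.1.8 and 2.1.3.8. Leave partner vasectomy to 4.2.1, as a contraceptive method with its condom and azoospermia assurance. The cost is two words in each of three criteria and, for a few more women at most, a urine or serum HCG test that is already on the schedule.
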